The Study's intervention group uses an aromatherapy inhaler, leading to a potential sensitivity to essential oils. Participants will be informed that in the case they have a sensitivity to essential oils, they need to stop using the inhaler and contact the Study PI immediately. The participant will be withdrawn from the Study and encouraged to see their healthcare provider.

There are no foreseeable participant risks or inconveniences related to participation in the research. The participants are free to withdraw at any time, and their decision to participate, refuse, or withdraw will have no impact on their treatment or any other relationship with SCCC. There is no economic burden for the participants.

The participant will be considered "lost to follow-up" if they stop communicating with the study team. The participant will also be considered "lost

to follow-up" if the participant's oncologist withdraws them from IV moderate to high emetogenic chemotherapy.

14) **Risks to Subjects***

Quality assurance will follow the University of Miami School of Nursing and Health Sciences quality assurance guidelines. These include minimizing potential harm for the participants.

The study measures include questions regarding well-being, some of which may cause emotional distress or discomfort. Participants will be informed that they may refuse to answer any question if they do not feel comfortable answering it. If a participant expresses or demonstrates emotional distress, the participant will be encouraged to contact the Sylvester Comprehensive Cancer Center (SCCC) Cancer Support Services for an appointment at [contact] or [contact].

The study's intervention group uses an aromatherapy inhaler, leading to a potential sensitivity to essential oils. Participants will be informed that in the case they have a sensitivity to essential oils, they need to immediately stop using the inhaler and contact the PI of the study, [name]. The participant will be withdrawn from the study and encouraged to see their healthcare provider.

There are no foreseeable participant risks or inconveniences related to participation in the research. The participants are free to withdraw at any time, and their decision to participate, refuse, or withdraw will have no impact on their treatment or any other relationship with SCCC. There is no economic burden for the participants.

Unanticipated Problems (Adverse Events and Serious Adverse Events) a) Definition of Unanticipated Problems

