> (1) The Office for Human Research Protections (OHRP) considers unanticipated problems involving risks to participants or others to include, in general, any incident, experience, or outcome that meets all the following criteria:

- 1. Unexpected in terms of nature, severity, or frequency given (a) the research procedures that are described in the protocol-related documents, such as the Institutional Review Board (IRB)-approved research protocol and informed consent document; and (b) the characteristics of the participant population being studied.
- 2. Related or possibly related to participation in the research ("possibly related" means there is a reasonable possibility that the incident, experience, or outcome may have been caused by the procedures involved in the research); and
- 3. Suggests that the research places participants or others at a greater risk of harm (including physical, psychological, economic, or social harm) than was previously known or recognized.

b) Unanticipated Problem Reporting: The investigator will report unanticipated problems (UPs) to the reviewing Institutional Review Board (IRB) as per institutional guidelines.

c) This study poses a low risk to study participants. However, psychological distress, aromatherapy inhaler sensitivity to essential oils, or a breach of confidentiality would constitute an adverse event.

(1) The psychological risk could be experienced if the participants believe that they are at high risk of breakdown or other stressors.

(a) Participants will be informed of their freedom to withdraw from the study at any time.

(i) If psychological distress is experienced: The PI will be notified, and study participants will be encouraged to contact the Sylvester Courtelis Center for Psychosocial Oncology and be given the appointment line for an appointment with a psychologist or psychiatrist.

(2) The study's intervention group uses an aromatherapy inhaler, leading to a potential sensitivity to essential oils.

(a) Participants will be informed that in the case they have a sensitivity to essential oils, they need to immediately stop using the inhaler and contact the PI of the study, [name].

(i) The participant will be withdrawn from the study and encouraged to see their healthcare provider.

d) The adverse event will be documented using the form HSR-4A: Internal nonserious adverse event log sheet.

(1) If a confidentiality breach occurs, the research team member will notify the PI immediately.

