(2) The principal investigator will investigate all AE & SAE.

(a) If the AE/SAE is 1) unexpected, 2) possibly related to the study, and3) is a greater risk to the participant or others or serious, the PI will notify the IRB within 5 business days.

(b) Only Grade 3 or higher AE/SAEs that are considered 'definite, probable, or possibly related' to the intervention (i.e., aromatherapy inhaler) will be captured.

15) **Potential Benefits to Subjects***

No direct benefit is anticipated for the participants in the control arm. The intervention group may experience some relief from the discomfort associated with CINV.

16) Vulnerable Populations*

This study will not include neonates, prisoners, children, or cognitively impaired adults. Pregnant women will not be excluded from this study; however, the study will not search for pregnant women. If a pregnant woman meets the

inclusion criteria, she will be allowed to participate if she so chooses. Pregnant participants may withdraw from the study at any time.

17) Multi-Site Research*

Not applicable.

18) Community-Based Participatory Research*

Not applicable.

19) Sharing of Results with Subjects*

This study will not share results with participants.

20) Setting

The study will be conducted at the SCCC's outpatient CTU located in South Florida. The study will include 100 oncology patients over 18 receiving moderate to high emetogenic chemotherapy regimens from various cancer diagnoses and stages.

Setting site:

1. Sylvester Main Medical Campus

[name]

21) **Resources Available**

Principal Investigator, [name], will oversee the study's management and manage communications with the IRB. [name] is a seasoned principal investigator and serves as Assistant Professor of Clinical at the University of Miami School of Nursing and Health Studies. [name] and the Co-PI will train the research team members to administer informed consent, self-reported questionnaires, and data management. She will assist with participant screening, consenting, data collection, and data management.

Co-Investigator, [name], is a registered nurse with more than 17 years of experience specializing in oncology patient care. She has participated in creating and developing nursing research studies for the past five years. She will take part in screening, making schedules, guiding patients through informed consent, and meeting patients to collect and process data.

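### The adverse-event rules in section 14 are not reconciled: the term *captured* is undefined and, if it governs the adverse-event record, leaves out Grade 1-2 oil sensitivity

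*Combined protocol and SAP*

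**What the plan says.** The relevant rules are in section 14 (Risks to Subjects), under Unanticipated Problems.

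- **Item c)** defines what counts: "psychological distress, aromatherapy inhaler sensitivity to essential oils, or a breach of confidentiality would constitute an adverse event". It sets no severity grade.
- **Item d)** sets the documentation rule: "The adverse event will be documented using the form HSR-4A: Internal nonserious adverse event log sheet". It states no limit by grade or by relation to the inhaler.
- **Item d)(1)** places one of the named events under the documentation item: "If a confidentiality breach occurs, the research team member will notify the PI immediately".
- **Item d)(2)** sets the investigation rule: "The principal investigator will investigate all AE & SAE". Again no limit is stated.
- **Item d)(2)(a)** sets the IRB-notification rule, which begins: "If the AE/SAE is 1) unexpected, 2) possibly related to the study". Relatedness here is to the study, and no grade is given.
- **Item d)(2)(b)** sets the capture rule: "Only Grade 3 or higher AE/SAEs that are considered 'definite, probable, or possibly related' to the intervention (i.e., aromatherapy inhaler) will be captured".

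Section 13 (Withdrawal of Subjects) tells participants with a sensitivity that "they need to stop using the inhaler and contact the Study PI immediately", and they are then withdrawn. Section 9 (Procedures Involved, Arm 2) and section 14 also provide for withdrawal. None of these places makes withdrawal depend on a grade.

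**The concern.** Item (b) is exclusive in its wording and sits inside item d), which deals with documentation. A study team member could reasonably take it as limiting what goes into the adverse-event record. Another could log every event named in c) on HSR-4A, as d) says. Each would be following the text, and the two records would differ.

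The event that matters most is oil sensitivity. It is the one harm specific to the product that the protocol names, and identifying it ends participation at any grade. Under the narrow reading, a participant could be withdrawn for something the protocol itself calls an adverse event while the captured record shows none. A later account of the inhaler's tolerability would then reflect the recording rule as well as what happened to participants.

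Little else in the plan would fill the gap. Section 12 marks safety data monitoring as not applicable, and the analysis plan in section 11 has no safety analysis. The diaries described in section 9 record use of antiemetics and aromatherapy and the relief obtained. The post-assessment, which asks about the inhaler and invites comments, is given only at the final visit.

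**Working it through.** There is no figure in the plan to reproduce and no arithmetic to do. The check sets the rules side by side and applies (b) to each named event.

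**Scope of each rule in section 14**

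| Item | Step | Grade limit | Relatedness limit |
|---|---|---|---|
| c) | names the adverse events | none | none (the inhaler appears only in naming oil sensitivity) |
| d) | document on HSR-4A | none | none |
| d)(2) | investigate | none | none |
| d)(2)(a) | notify the IRB | none | possibly related to the study (plus other conditions) |
| d)(2)(b) | capture | Grade 3 or higher | at least possibly related to the inhaler |

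**Applying (b), on the assumption that it governs the adverse-event record**

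1. *Oil sensitivity.* The relatedness condition is met, so grade decides. Grade 3 or higher is captured; Grade 1-2 is not. Under d) it would be documented at either grade. Under sections 9, 13 and 14 it leads to withdrawal at either grade.
2. *Psychological distress.* Both conditions must be met, so it is captured only if it is Grade 3 or higher and attributed to the inhaler. Section 14 also gives a source other than the inhaler: "The study measures include questions regarding well-being, some of which may cause emotional distress or discomfort". Distress from that source would not be captured. Under d) distress is documented without these conditions.
3. *Confidentiality breach.* It does not arise from the inhaler and is not a clinically graded event, so it is not captured. Under d) and d)(1) it belongs to the documentation item.

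**Applying (b), on the assumption that it governs some other record**

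If capture means, for example, entry in the study database, and the HSR-4A log is separate, all three named events are still documented under d) and nothing conflicts. The same holds if (b) is meant only for events that c) does not name. No supplied text states either arrangement.

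**Result.** Whether the rules conflict turns on one undefined word. Under one reading the named events are recorded in full; under the other, mild and moderate oil sensitivity drops out of the record.

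**The case against.** The strongest reply is that this is an ambiguity and not a proven contradiction. Section 14 uses different verbs for different steps: document, investigate, notify, capture. They collide only if capturing an event means logging it on HSR-4A. There is some textual reason to doubt that: the form's title confines it to nonserious events, whereas (b) speaks of AEs and SAEs together, so (b) may describe a different record. The form and the institutional guidelines that item b) invokes were not supplied and might settle the term. This objection stands in part. It lowers confidence and rules out calling the text a flat contradiction. It does not remove the need to say which reading is meant.

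A second reply is that handling is already secure. Sensitivity must be reported, goes to the PI and ends participation at any grade. That is correct, and the point is confined to the record.

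A third is that the harm is hypothetical, since no adverse-event table or safety endpoint is planned. That also stands, and it is why the point is minor.

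A reader might infer more than the text supports:

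- *That leaving out control-arm events is an inconsistency.* Only the intervention arm has an inhaler, so a rule confined to inhaler-related events will ordinarily leave the control arm out. That is a design choice.
- *That the notification rule in (a) conflicts with (b).* Notification to the IRB and capture in study data may properly have different scopes. An event that meets (a) is notified whether or not (b) captures it.
- *That a fixed share of the named event types is lost.* Item c) names psychological distress in general, which could in principle be severe and attributed to the inhaler. Treating it as wholly excluded would substitute the narrower category of distress caused by study questions. A count of categories would not measure impact in any case.

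**Conclusion.** The point holds as an unreconciled set of recording rules. Items c), d) and d)(2) define, document and investigate adverse events without a grade limit; d)(2)(b) confines capture to Grade 3 or higher inhaler-related events, and no supplied text says how the two fit together. Followed as written and taken to govern the adverse-event record, (b) would drop Grade 1-2 oil sensitivity and confidentiality breaches, and would drop distress unless it is both Grade 3 or higher and attributed to the inhaler.

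Severity is minor. The efficacy analyses do not use this record, and safety is not among the listed endpoints. No number of participants affected can be given, because the documents contain no rate for any of these events.

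Confidence is moderate. The conclusion that the rules need reconciling rests only on the text. The conclusion that events would go unrecorded rests on the assumption that (b) governs the adverse-event record. It would be wrong to infer that sensitivity would go unnoticed or unmanaged, because reporting, investigation and withdrawal are all specified.

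**What to change.** Reconcile the passages in section 14:

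- Define what it means for an event to be captured in d)(2)(b), and name the record it refers to.
- State that (b) does not limit the HSR-4A documentation under d) of the events named in c). Oil sensitivity in particular would then be logged at any grade, with its attribution.
- State that sensitivity events and the withdrawals that follow from them will be counted in the results.

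The IRB-notification and withdrawal rules stay as they are. The change concerns recording only.

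The cost is a sentence or two of protocol text and additional entries on a form the protocol already names. How many entries cannot be estimated. The protocol sets no threshold for psychological distress, the planned sample is 100 patients receiving chemotherapy, and logging distress in both arms could add more than oil sensitivity alone would.

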[name] BSN, CHRN, RN, has been a nurse at the University of Miami since 1994. [name] is a Hyperbaric Safety Director for 15 years. She will be assisting with patient screening, patient education, consenting process, and data entry.

[name], BSN, RN, CCRC, is a registered nurse with extensive clinical research coordinator experience. She will be assisting with patient screening, patient education, consenting process, and data entry.

[name], is a bilingual oncology nurse at the University of Miami Sylvester Comprehensive Cancer Center with extensive experience in

administering chemotherapy and biological therapy for over 9 years. She has served as a charge nurse in the CTU area for the last 4 years. She will be assisting with patient screening, patient education, consenting process, and data entry.

22) **Prior Approvals**

•

The study team received approval for using the CD-RISC, FACT-G questionnaires, and the Soothing Scents Company's QueaseEASE aromatherapy inhaler product (see associated documents). All other instruments are open to the public and are free to use.

23) **Recruitment Methods**

This two-arm control trial study will be conducted at the Sylvester Comprehensive Cancer Center (SCCC) main, campus in the Comprehensive Treatment Unit (CTU). The study will identify cancer patients that are undergoing moderate to high emetogenic chemotherapy regimens by screening upcoming patients scheduled chemotherapy visits. The study team members will review potential participants' daily schedule notes to screen the potential participants by the study inclusion criteria. If the potential participant meets the inclusion criteria for the study, the study team member will verify and meet the potential participants on their next treatment appointment in the CTU.

- i. Recruitment flyers will be posted at the SCCC main campus. The recruitment flyers will provide information about the study, eligibility criteria, and contact information. If a potential participant calls the contact person on the recruitment flyer, the study team member will explain the study to them. If the participant is interested and meets the eligibility criteria, the study team member will verify the next scheduled chemotherapy infusion visit and confirm the visit with the potential participant. At this time, the study team member will explain that the informed consent process will take place on their next scheduled chemotherapy infusion.
- ii. Potential participants will be identified using the weekly SCCC's CTU schedule notes, displaying patients' chemotherapy regimen summary (e.g., chemotherapy drug type, dosage, and frequency). The study team member will identify patients undergoing moderate to high emetogenic chemotherapy (adjuvant or neoadjuvant). Identified patients will be screened for eligibility criteria by reviewing the patients' medical records. If a patient meets all eligibility criteria, a study team member will approach the patient during their regular outpatient CTU visit and screen for essential oils sensitivity. In case the potential participant is interested and willing to consent immediately, the study team member will review the study's informed consent. Once the informed consent is

> signed, the participant will receive a copy of the informed consent form. If the potential participant needs additional time to think about the study, the study team member will follow up with the patient at their next scheduled chemotherapy infusion visit. At this time, if the potential participant is interested and still meets the eligibility criteria, the study team member will explain the study and review the informed consent process.

24) Local Number of Subjects

The total single-site sample size is 100 participants.

25) Confidentiality

All participants will be assigned a unique study ID number. Identifying information will be stored separately from other study data in a passwordprotected, encrypted Excel file. All data will be stored on secure servers at the University of Miami, Box. Additionally, the REDCap software will be utilized during the study to maximize data security. Only authorized study personnel will have access to identifying information throughout the study.

Choose the statements below that are applicable to this research:

26(a). Will the research collect protected health information or personally identifiable information from the EMR or from subjects at UHealth and/or JHS?

 \boxtimes Yes (If checked go to 26(b))

□ No (If checked, go to Section 27)

26(b). Check the box next to the correct statement below

Research Subjects will sign a HIPAA Authorization before the research will collect this data.

Research Subjects will not sign a HIPAA Authorization for this data collection and the research is requesting a waiver of HIPAA authorization from the IRB

26(c). How will the research store the data?

On a University of Miami electronic device (e.g. encrypted, password-protected computer)

On a cloud-based storage system that is approved by the University of Miami

On the secured JHS SharePoint environment

Other, specify: Click here to enter text.

26(d) Select one of the following:

The Principal Investigator (and/or Study Team members) will record (e.g. write down, abstract) data acquired in a manner that does not include any indirect or direct identifiers (listed

in the instructions for Section 26 of this protocol), and the recorded data will not be linked to the individual's' identity.

OR

The Principal investigator (and/or Study Team members) will record (e.g. write down, abstract) the data collected in a manner that does not include any direct identifiers (see list in the instructions for Section 26 of this protocol) of any subject. Instead, the Principal Investigator and/or Study Team members shall will assign a code (that is not derived in whole or in part from any direct or indirect identifiers of the individual) to each study subject and link the code to the study subject's identity. The link to each subject's identity and/ or other identifiable information will be maintained on a document separate from the research data.

26(e) Additional requirement for Jackson Health System Data:

Not-applicable, no data will be acquired from JHS under a waiver of authorization.

☐ JHS data, including Protected Health Information (PHI) and/or Personally Identifiable Information (PII), acquired from JHS for this research under a waiver of authorization shall only be stored on the secured JHS SharePoint environment made available by JHS. I and the Study Team members shall not copy or store the JHS sourced personally identifiable information (PII), including protected health information (PHI) data to any other system, including any systems maintained or provided by the University of Miami. I and the Study Team shall only copy or transfer JHS-sourced data that has been properly de-identified in accordance with all requirements contained in the HIPAA Rules by removing all of the identifiers listed in the instructions for Section 26 of this protocol.

27. Biospecimens

- Not applicable. No biospecimens will be collected
- *Bio*-Specimens obtained for this research will be stored without any direct or indirect identifiers.
- *Bio*-Specimens obtained for this research will be stored in a de-identified coded manner.

When required to transport data or bio-specimens for this research, the research team will transport the data and bio-specimens in a de-identified (or anonymous) manner with a link to the individual subject's identity maintain separately from the data and/or bio-specimen.

26) **Provisions to Protect the Privacy Interests of Subjects**

The study team member will take steps to ensure that the participants' privacy is protected. The study team member will introduce, explain, and answer any questions

related to the study. The study team member will explain that medical information will be de-identified for the study. All participant demographic information and collected data will be encoded for confidentiality in REDCap. Participants will be assigned a number that will be utilized to track their data throughout the study. No participant personal identifying information will be utilized to share data among personnel or to analyze results from assessments. The PI and Co-PI will be responsible for assigning participant codes for data tracking and randomization. This will be done utilizing an online pseudo-random number randomizer (https://www.randomizer.org/) (Urbaniak & Plaus, 2013).

27) Compensation for Research-Related Injury

This section is not applicable. The risks of this study are minimal.

28) Economic Burden to Subjects

This section is not applicable. There is no cost to the participants.

29) **Consent Process**

All participants are required to provide informed consent before the beginning of study procedures. The informed consent will occur at the SCCC's outpatient CTU on the patients' chemotherapy infusion visit in their quiet, comfortable setting. The consent, all study procedures, and materials will be available and completed in the participant's preferred language (English or Spanish) by a study team member fluent in the preferred language (English or Spanish). Potential participants will receive a full explanation of the study, including the study's purpose, procedure, and risks/benefits. The study team member will also explain that participation is voluntary at no cost; all study information is kept confidential, and that they may withdraw from the project without penalty or any monetary loss. Potential participants will have ample time to ask any pertinent questions related to the study. After answering all their questions, and the potential participant understands the study information, a study team member will go through the informed consent process in the participant's preferred language. The study team member will allow the participant to decide whether they want to participate. Once the informed consent is signed in REDCap, a copy will be provided to the participant, the signed consent will be uploaded to the participant's electronic medical record, and sent via encrypted email to the treating oncologist notifying them of the patient's consent to participate in the study. The study team member will provide the study's contact information should the participant have any additional questions during the study.

Non-English-Speaking Subjects

The consent, all study procedures, and materials will be available and completed in the participant's preferred language (English or Spanish) by a study team member fluent in the preferred language (English or Spanish).

30) **Process to Document Consent in Writing**

All recruited participants will sign the informed consent before receiving the study's instructions, assessments, and packet. The consent and data will be stored in the password-protected University of Miami's secure server, REDCap.

Type of Request:

- Waiver of Authorization for access to medical record for subject identification/recruitment.
 - Waiver of Authorization for access to medical record to obtain data for the research.

